6. TREATMENT COMPARISONS

6.1. Data Display Treatment

Data display treatment descriptors with actual treatment description will be defined as shown below:

Study Part	Treatment Description	Treatment Display Code
Part 1	Part1:EIDD-2801 200 mg BID	А
	Part 1: Placebo	В
Parts 2/3/4/5/6/7/8/9	Parts 2-9:EIDD-2801 200, 400, or 800 mg BID	C/E/G/I/K/M/O/Q
	Parts 2-9: Placebo	D/F/H/J/L/N/P/R
Pooled	EIDD-2801 200 mg BID	1
Treatment	EIDD-2801 400 mg BID	2
	EIDD-2801 800 mg BID	3
	Placebo	9

7. STUDY POPULATION

7.1. Subject Disposition

A summary table will be generated by study part and treatment to provide the following:

- Number of subjects Randomized (ITT)
- Number of subject randomized and not treated
- Number and percentage (based on ITT) of subjects in the Safety population
- Number and percentage (based on Safety) of subjects in the mITT population
- Number and percentage (based on Safety) of subjects in the PK population
- Number and percentage (based on Safety) of subjects in the PP population
- Number and percentage of subjects in the safety population who completed the study
- Number and percentage of subjects in the safety population who completed the Treatment
- Number and percentage of subjects in the safety population who discontinued the study
- Reason for discontinuation of study

A subject listing noting treatment and study duration and reason for withdrawal from the study will be provided. Randomization details will be provided in the listing. A separate table will be provided by pooled treatment group to provide the following:

- Number of subjects in the Safety population
- Number and percentage of subjects in the mITT population
- Number and percentage of subjects in the PK population
- Number and percentage of subjects in the PP population
- Number and percentage of subjects in the safety population who completed the study
- Number and percentage of subjects in the safety population who completed the Treatment
- Number and percentage of subjects in the safety population who discontinued the study

• Reason for discontinuation of study

For subjects excluded from PP population, reasons for exclusion will be listed.

7.2. **Protocol Deviations**

Protocol deviations will be summarized and listed. All important protocol deviations, potentially leading to exclusion from the PP population, will be reviewed prior to database lock and unblinding. The reason for exclusion from PP will be documented and approved before unblinding.

7.3. Demographic and Baseline Characteristics

Demographic (age, sex, race, and ethnicity) and baseline characteristics (height, weight, and body mass index [BMI], vital signs, Smoking Status (current Smoker, ex-smoker or Non-smoker), Days from Symptom Onset, D-dimer, CRP levels, WBC absolute neutrophils count and absolute lymphocyte count) will be summarized and listed.

The baseline viral RNA, baseline patient reported symptom will be summarized and listed.

Demographic and baseline characteristics will be summarized for the ITT population by study part and treatment, and separately for the safety population for the pooled analyses.

7.4. Medical History

Medical history findings will be coded using Medical Dictionary for Regulatory Activities (MedDRA) Version 23. Medical history will be summarized by the number and percentage of subjects within each SOC and PT.

Ongoing medical conditions that are at increased risk for severe illness from COVID-19 will be reviewed and summarized separately.

7.5. **Prior and Concomitant Medications**

Medications used prior to the first dosing date of study drug will be recorded as prior medications. Medications used on or after the first dosing date of study drug and during the study will be recorded as concomitant medications.

Non-study medications will be coded to the medicinal product name using the World Health Organization Drug Dictionary (WHO-DD Version March 2017).

Prior and concomitant medications will be summarized using Anatomical Therapeutic Chemical (ATC) Level 2 and Level 4 coded terms.

8. SAFETY ANALYSES

The safety data including AEs, clinical laboratory data, and vital signs will be summarized using descriptive statistics and listed individually for each subject.

8.1. Extent of Exposure

Exposure duration in number of days will be summarized. The exposure duration is derived as (the date of last dose – the date of first dose+1).

The number and percentage of subjects with number of doses received in the following categories will be summarized for the Safety population:

- ≥ 1 and < 5 doses
- $\geq 5 \text{ and } \leq 9 \text{ doses}$
- 10 Doses

Dosing records will be listed. A separate listing will be provided for subjects who did not complete the treatment (receiving all 10 doses) with reasons for each dose missed.

8.2. Adverse Events

Adverse events will be coded using MedDRA[®] (Medical Dictionary for Regulatory Activities) Version 23. Any events reported after the initiation of study treatment and up to 14 days after the last dose of study treatment are defined as treatment-emergent AEs (TEAEs). AEs started more than 14 days after the last dose of study treatment will be considered post treatment and will be summarized separately

Adverse event summarizes will summarize only TEAEs. Adverse events will be categorized by TEAE, serious TEAE (SAE), death, and discontinuation. These categories will be further summarized by the causal relationship to study drug (Related and Possible related will be grouped together as Related; AEs Reported as Unlikely and Not Related will be grouped together as Not Related).

The Investigator will provide an assessment of the intensity of each AE. Intensity will be assessed in terms of severity (mild, moderate, severe, potentially life-threatening or death). Subjects will be counted once and summarized under their highest severity within a SOC and PT.

The following TEAE summary tables will be prepared:

• Overall Summary of TEAEs (Any TEAE, TEAE Related to study drug, Grade 2 or higher TEAE, Grade 3 or higher TEAE, Drug related TEAEs, Drug related Grade 3 or higher

TEAE, TEAEs leading to study drug discontinuation, Drug related TEAEs leading to study drug discontinuation, Serious TEAE, TEAE leading to death)

- Summary of TEAEs by SOC and PT
- Summary of TEAEs by maximum severity SOC, and PT
- Summary of Grade 2 or higher TEAEs by SOC and PT
- Summary of Grade 3 or higher TEAEs by SOC and PT
- Summary of Drug Related Grade 3 or higher TEAEs by SOC and PT
- Summary of Drug Related TEAEs by SOC, and PT
- Summary of TEAEs resulting in discontinuation from study drug by SOC and PT
- Summary of Drug Related TEAEs resulting in discontinuation from study drug by SOC and PT
- Summary of Serious TEAEs by SOC and PT
- Summary of Drug Related Serious TEAEs by SOC and PT
- Summary of Post Treatment AEs by SOC and PT

8.3. **Pregnancies (as applicable)**

If any female subjects become pregnant during the study, a listing will be provided.

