10.7.3.1. Primary Outcome Measures

Virologic Efficacy: The distribution of days until first non-detectable SARS-CoV-2 viral RNA in NP swabs will be estimated for each randomized arm (drug versus placebo), using Kaplan-Meier methods with a corresponding exact stratified log-rank test (Part 1 only: to account for the "early" versus "late" time from symptom onset randomization strata). "Non detectable" will be defined as a viral load below the limit of quantification (BLOQ). Two consecutive non-detectable viral RNAs in NP swabs (or one negative with no further follow-up) will be required to achieve the event. The date of the first non-detectable will be the event date. Participants who prematurely discontinue the study before achieving non-detectable results will have follow-up for efficacy endpoints censored at the date of last measurement. Losses to follow-up will be assumed non-informative.

Safety and Tolerability: In order to measure the safety and tolerability of EIDD-2801, we will estimate by randomization arm the probability of 1) any AEs leading to early discontinuation of blinded treatment (active or placebo), 2) study drug-related discontinuation of treatment, 3) new grade 3 or higher AE (not already present at baseline), and 4) study drug-related new grade 3 or higher AE. The cumulative probability (i.e., risk) of each safety and each tolerability endpoint (4 endpoints) will be estimated using the Kaplan-Meier approach and stratified log-rank test will be employed for between trial arm comparisons (as outlined for the primary efficacy outcome). Follow-up will be right censored at the date of last known status and event times will be the date of first onset of the given endpoint (e.g., time to first AE leading to early discontinuation of blinded treatment).

The safety and tolerability profile of EIDD-2801 in humans is currently not fully characterized and descriptive participant-level listings of safety and tolerability events will be summarized. We will estimate 28-day risk function of each safety and tolerability endpoint with a corresponding 2-sided 90% confidence interval, with focus on the upper confidence limit for interpretation of results. To inform the design of future larger trials we will estimate the difference in probabilities

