10.7.3.2. Secondary Outcomes

Safety: Occurrence of Grade 2 or higher AEs and drug related AEs will be evaluated using the same approach as outlined for the primary safety analysis in Section 10.7.3.1. We will describe and estimate all-cause mortality and hospitalization during the 28-day period from and including the day of the first (confirmed) dose of study treatment. The Kaplan-Meier approach described above will be applied to the endpoint of days until first hospitalization or death, and the 28-day risk function will be estimated as described for the primary safety endpoints.

Duration of fever, duration of symptoms, and duration of time to self-reported return to usual health will be summarized with descriptive statistics. Participant-specific durations of fever and symptoms will be compared between study arms using a stratified Wilcoxon rank-sum test. The distribution of days until improvement of all new or worsened COVID-19 symptoms will be compared between study arms using Kaplan-Meier methods with a corresponding exact stratified log-rank test (to account for the "early" versus "late" time from symptom onset randomization strata). New or worsened symptoms of COVID-19 may include feverishness, chills, myalgias, headache, sore throat, loss of sense of smell, loss of sense of taste, cough, and difficulty breathing. Improvement in these symptoms is defined as a decrease in all new or worsened symptoms (i.e., from severe/moderate severity to mild/absent/pre-COVID-19 severity, or a decrease in mild severity to absent). Participants who do not have complete symptom diaries due to hospitalization or death will be ranked in these analyses as having poorer outcomes than participants who survived without hospitalization.

Analyses for the additional objectives will be described in the SAP.

Virologic: The distribution of days until first non-detectable SARS-CoV-2 in NP swabs (i.e., infectious virus measurement) will also be estimated for each randomized arm (drug versus placebo), using Kaplan-Meier methods with a corresponding exact stratified log-rank test (to account for the "early" versus "late" time from symptom onset randomization strata). Participants who prematurely discontinue the study before achieving nondetectable results will have follow-up for efficacy endpoints censored at the date of last measurement. Losses to follow-up will be assumed non-informative.

Protocol EIDD-2801-2003 Ridgeback Biotherapeutics LP

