2.2. Study Endpoints

2.2.1. Primary Endpoint

- The viral RNA negativity determined by reverse-transcriptase polymerase chain reaction (RT-PCR) of NP swabs
- Any adverse events (AEs) leading to early discontinuation of treatment; study drugrelated discontinuation of treatment; new Grade 3 or higher AEs (not already present at baseline); study drug-related new Grade 3 or higher AEs and serious AEs

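### The graded, drug-related and serious AE tables in SAP 8.2 stop 14 days after last dose, so they cannot give 28-day counts for two Part 1 primary safety endpoints; SAP section 11 does not declare this

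*SAP*

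**What the plan says.** **Protocol, Part 1.** Section 10.7.3.1 names four primary safety and tolerability endpoints. Two concern treatment discontinuation; the other two are new Grade 3+ AEs and drug-related new Grade 3+ AEs. For all four it states: "We will estimate 28-day risk function of each safety and tolerability endpoint". A two-sided 90% confidence interval goes with each, "with focus on the upper confidence limit for interpretation of results", and follow-up is censored at last known status. Section 10.7.3.2 extends this to the secondary endpoints: "Occurrence of Grade 2 or higher AEs and drug related AEs will be evaluated using the same approach as outlined for the primary safety analysis".

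**Protocol, pooled analyses.** Section 10.8 calls an AE treatment-emergent if it begins or gets worse after the first dose. It gives no end date.

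**SAP.** Section 2.2.1 keeps the Grade 3+ endpoints as primary, adds serious AEs and states no time limit: "new Grade 3 or higher AEs (not already present at baseline); study drug-related new Grade 3 or higher AEs and serious AEs". Section 8.2 then counts as treatment-emergent those events "after the initiation of study treatment and up to 14 days after the last dose of study treatment are defined as treatment-emergent AEs", and adds: "Adverse event summarizes will summarize only TEAEs". For the remainder it says: "AEs started more than 14 days after the last dose of study treatment will be considered post treatment and will be summarized separately". The only table listed for these is "Summary of Post Treatment AEs by SOC and PT".

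**Declared changes.** The SAP introduction undertakes to point out substantial departures from the protocol's statistical section. Section 11 lists the unstratified log-rank test, the dropped Part 1 safety comparisons and the descriptive presentation of safety data. It does not mention the AE window.

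**The concern.** Participants are followed, and AEs collected, to Day 28, and the protocol sets 28 days as the horizon for the Part 1 safety endpoints. The tables that would report two of those endpoints stop earlier.

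The post-treatment table does not close the gap. It carries no grade, relatedness or seriousness, so a late Grade 3 event cannot be told from a late Grade 2 event. Nor can it be added to the treatment-emergent tables, because one subject may appear in both.

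The same limit applies to the secondary Grade 2+ and drug-related AE endpoints, and to serious AEs over full follow-up (for serious AEs the documents set no 28-day horizon). At stake is whether a reader of the study report sees the complete count for a primary safety endpoint and is told if the period was shortened.

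**Working it through.** **1. The plan's own horizon.** 5 days on treatment + 23 days off = 28 days (protocol and SAP section 3). This agrees with the 28-day risk in protocol 10.7.3.1.

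**2. Where the window ends.** SAP 5.5.1 counts the first dose as Day 1. Window end = day of last dose + 14; days outside = 28 − window end. The last dose falls on Day 5, or on Day 6 where the dosing footnote allows it. Days 1 and 3 are shown as examples of stopping early.

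| Last dose | Window ends | Days outside | Share of 28 days |
|---|---|---|---|
| Day 5 | Day 19 | 9 | 32.1% |
| Day 6 | Day 20 | 8 | 28.6% |
| Day 3 | Day 17 | 11 | 39.3% |
| Day 1 | Day 15 | 13 | 46.4% |

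These are shares of calendar days, not of events. Because the cut runs from last dose, those who stop early are covered for less time, so the length of the window depends on tolerability and could differ by arm.

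**3. What the listed tables can yield.**

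| Needed over 28 days | Up to window end | After window end |
|---|---|---|
| Grade 3+ AE | treatment-emergent table | not separable by grade |
| Drug-related Grade 3+ AE | treatment-emergent table | not separable by grade or relatedness |
| Grade 2+ AE; drug-related AE | treatment-emergent tables | not separable by grade or relatedness |
| Serious AE; fatal AE | treatment-emergent tables | not separable by seriousness or outcome |

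Protocol 7.2 requires recording of Grade 2+ events and of events that change treatment. The post-treatment table will therefore hold mainly Grade 2+ events, and Grade 3+ is what it cannot isolate. The two discontinuation endpoints are essentially unaffected, since dosing ends by Day 5 or 6.

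**4. Size under an assumption.** The documents give no timing of events. Assume a constant hazard and a true 28-day risk of 10%. The risk seen by window end is then 1 − 0.90^(19/28) = 6.90% for Day 19, and 1 − 0.90^(20/28) = 7.25% for Day 20. If Grade 3+ events cluster early, less is missed.

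**5. Leverage of one event, as an illustration.** The exact two-sided 90% upper limit is the 95th percentile of Beta(x + 1, n − x). With n = 22 and no censoring:
- x = 1: Beta(2, 21) gives 19.8%
- x = 0: 1 − 0.05^(1/22) = 12.7%

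**6. A related wording conflict.** The partial-date rule in SAP 5.6 has no window end. Take a first dose on 10 March and a last dose on 14 March (Day 5), so the window closes on 28 March (Day 19). An AE dated only April is imputed to 1 April (Day 23). It is post treatment under 8.2 but treatment-emergent under 5.6. This is an edge case.

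**The case against.** The strongest reply is that the SAP overrides the protocol and plans only descriptive safety (SAP 2.3 and 11), so the protocol's 28-day risk with its 90% interval is no longer a planned output. That stands in part. A reader might infer that a planned confidence limit will come out too low; the documents do not support this, because the SAP plans no confidence limit for AEs. But *descriptive* says how results are shown, not over what period: a 28-day count is also descriptive, and section 11 is silent on the period.

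A reader might also infer that late AEs are lost. They are not. SAP 8 lists AEs by subject, and the post-treatment table shows them. Laboratory grading in SAP 8.4 has no 14-day limit, and hospitalization, oxygen outcomes and death are handled in SAP 9.4 to 9.6. Under protocol 7.3.3 a first onset two weeks or more after a short course would seldom be judged related. All this narrows the gap, but none of it supplies a summary count for the endpoint.

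Section 8.2 says *reported* for treatment-emergent events and *started* for post-treatment ones. Read literally, that could leave some events in neither class. The onset-date logic of SAP 5.6 and the word *started* itself make onset the evident criterion, so this is a wording point only.

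Finally, a 14-day window with separate later reporting is a choice the SAP may make, and the display contents are in a separate document that was not seen. Both points are fair. The conclusion is therefore confined to the tables listed in 8.2 and to the missing declaration.

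**Conclusion.** The point holds as a reporting and disclosure gap. Followed as written, the summary tables listed in SAP 8.2 can omit late Grade 3+ AEs from two Part 1 primary safety endpoints, and late serious AEs from the endpoint that SAP 2.2.1 enlarges. The period also departs from protocol 10.8, and section 11 does not say so.

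The effect is probably small. It is confined to late-onset, non-laboratory Grade 3+ or serious AEs not already captured as hospitalization, oxygen or death outcomes. Their number is unknown, and the text gives no ground for claiming a material difference between arms. An AE that begins inside the window and later worsens or proves fatal is not classed as post treatment. The constant-hazard figures rest on an assumed risk and assumed timing, and the upper limits only show how much one event weighs in an arm of 22. The correction is still worth making, because these are primary endpoints, the arms are small and the data are in hand.

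**What to change.** Keep the 14-day treatment-emergent window if wanted, and add one overall summary of Grade 2+, Grade 3+, drug-related, drug-related Grade 3+, serious and fatal AEs from first dose through Day 28 or end of study, counting each subject once per class. Alternatively, break the post-treatment table down by grade, relatedness and seriousness, and flag subjects who already had a treatment-emergent event of that class, so that the 28-day count can be recovered.

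Declare the window in section 11. As a clean-up, use onset date on both sides of the cut in 8.2 and apply the same window end in the 5.6 partial-date rule.

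The cost is SAP wording, one date cut-off in programming and a few extra tables; no new data are needed. The downside is that the added tables will include some late, possibly disease-related events.

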8.4. Clinical Laboratory Evaluations

Individual data listings of laboratory results will be presented by study part, treatment, subject, and time point. Values outside of the laboratory's reference range (i.e., those with high or low values) and lab toxicity grade will be included in the laboratory listings.

Quantitative values and change from baseline in quantitative values will be summarized by planned nominal time and treatment for each quantitative lab. For Laboratory data reported with "<" or ">" symbols, data will be presented in listings with their inequality symbols; however, for tabulation of summary statistics, the number associated with the inequality sign will be used for analysis.

Laboratory abnormalities will be graded according to the DAIDS Table for Grading the Severity of Adult and Pediatric Adverse Events Corrected Version 2.1, if applicable.

Any graded abnormality that occurs following the initiation of study drug and represents at least a 1-grade increase from the baseline assessment is defined as treatment-emergent. The number and percentage of subjects experiencing treatment-emergent graded laboratory abnormalities will be summarized. Laboratory abnormality shifts from baseline to worst post-baseline assessments will also be summarized for the treatment emergent abnormality. A summary of treatment emergent Grade 3 and Grade 4 laboratory abnormalities by treatment will also be provided.

Clinical Important LAB Findings

- Platelets less than 50K
- lipase >3xULN

Liver Function Test

Liver Function tests (Alkaline Phosphatase, ALT, AST, Total or Direct Bilirubin and GGT) will be summarized separately. Evaluation of drug-induced serious hepatotoxicity (eDISH) with log-log plots of peak post-baseline TB (x ULN) vs. peak post-baseline AST /ALT (x ULN) will be provided by treatment group.

The number and (%) of subjects meeting the following criteria will be summarized by treatment group based on the liver function tests including the following:

- ALT \geq 5xULN, \geq 10xULN, and \geq 20xULN
- AST \geq 5xULN, \geq 10xULN, and \geq 20xULN
- Total bilirubin≥2×ULN
- ALT or AST >3xULN and Bilirubin >2xULN

8.5. Other Safety Measures

8.5.1. Vital Signs

Vital sign assessments will be performed at the time points specified in Table 1. Vital sign results will be listed subject, and time point. Vital signs will be summarized using descriptive statistics (n, mean, SD, median, min, and max) over time in terms of absolute values and changes from baseline at each scheduled time point for the safety analysis set.

8.5.2. Inflammatory Markers

Lab tests collected for inflammatory markers and immune responses will be summarized and listed.

9. EFFICACY ANALYSES

9.1. Efficacy Analyses

SARS-CoV-2 RNA

The actual and change from baseline in SARS-CoV-2 RNA (log 10) will be summarized by treatment and visit in tabular and graphic format using descriptive statistics for each specimen type. Individual SARS-CoV-2 RNA over time will be plotted by treatment.

Treatment comparisons between each active dose group and placebo group in SARS-CoV-2 RNA change from baseline will be analyzed using a mixed model for repeated measures (MMRM) with restricted maximum likelihood estimation and an unstructured covariance matrix. This model corrects for dropout and accounts for the fact that measurements taken on the same subject over time tend to be correlated, by using all available information on subjects within the same covariate set to come up with an estimate of the treatment effect for a dropout free population. The statistical model will be fitted with terms for treatment group, visit, treatment by visit interaction, baseline SARS-CoV-2 RNA and baseline SARS-CoV-2 RNA by Visit interaction. The estimated treatment difference for "Active – Placebo" at each visit will be displayed in the summary of statistical analysis together with the 95% confidence interval and the associated p-value. Least Squares Means for each visit will also be presented with the standard error. Least Squares Means and estimated treatment differences for each visit and the associated 95% confidence interval will be displayed graphically.

Sensitivity analyses will be conducted using an Analysis of Covariance (ANCOVA) model with terms for treatment group and baseline SARS-CoV-2 RNA by each study visit. The estimated treatment difference for "Active – Placebo" at each visit will be displayed in the summary of statistical analysis together with the 95% confidence interval and the associated p-value. Least Squares Means for each visit will also be presented with the standard error. If parametric assumptions are violated, non-parametric tests (e.g., extended Mantel-Haenszel test) may be utilized to provide a p-value for sensitivity analysis.

The number and percent of subjects with SARS-CoV-2 RNA of \leq LLOQ, or SARS-CoV-2 RNA reduction of \geq 1, 2, or 3 log₁₀ from baseline will be presented for each treatment group by visit. P-values for between-group comparison may be included as descriptive statistics using a 2 sample binomial test.

Time to response un-detectable Viral RNA will be summarized using Kaplan-Meier method. The median time to response and the cumulative probability of response by visit along with the 95% confidence intervals will be provided by treatment group.

The baseline adjusted average area under curve (AAUCMB) through Day 3, Day 5, Day 7, Day 14 and Day 28 will be derived and summarized by treatment group. Between groups comparisons will be performed using an ANCOVA model with terms for treatment group and baseline SARS-CoV-2 RNA. The estimated treatment difference for "Active – Placebo" at each visit will be displayed in the summary of statistical analysis together with the 95% confidence

interval and the associated p-value. Least Squares Means for each visit will also be presented with the standard error.

The number and percent of subjects with negative infectious virus isolation based on qPCR assay will be summarized for each treatment group by visit. P-values for between-group comparison may be included as descriptive statistics using a 2 sample binomial test.

Time to negativity of infectious virus isolation will be summarized using Kaplan-Meier method. The median time to response and the cumulative probability of response by visit along with the 95% confidence intervals will be provided by treatment group.

